7.3 Exclusion Criteria

Subjects having any of the following criteria, either at screening or at baseline, will not be included in the study:

- 1. Has received surgical permanent implants, grafting, or surgery below the eyes on the face prior to injection or lower lid blepharoplasty within 6 months prior to injection.
- 2. Has received within the specified (washout) period or plans to receive treatment during the study conduct with a non-permanent facial filler in any facial area below the eyes:
 - a) 12 months prior to study start hyaluronic acid [HA] or collagen
 - b) 18 months prior to study start calcium hydroxylapatite [CaHA]
- 3. Has received at any time or plans to receive during the study a permanent facial filler (e.g. poly L-lactic acid [PLLA], polymethyl-methacrylate [PMMA], silicone) below the eyes.
- 4. Has received within the past 6 months or plans to receive during the study facial dermal resurfacing procedures (e.g. chemical peel, dermabrasion, ablative laser resurfacing), non-invasive skin-tightening (e.g. Thermage), botulinum toxin injections, mesotherapy, or fat injections below the eyes.
- 5. Has received in the past 2 weeks or plans to receive during the study any prescription wrinkle therapies (e.g. RENOVAÒ), topical steroids, skin irritating topical preparations, or pigmenting agents (self-tanning agents) for use on the face.
- 6. Has received in the past 2 months, or plans to receive immunosuppressive medications or systemic steroids (intranasal/inhaled steroids acceptable) during the study.
- 7. Has an acute inflammatory process or infection, active herpes infection, or history of chronic or recurrent infection or inflammation with the potential to interfere with the study results or increase the risk of adverse events (AEs).
- 8. Has a known bleeding disorder or has received or is planning to receive anticoagulation, anti-platelet, or thrombolytic medications (e.g., warfarin), antiinflammatory drugs (oral/injectable corticosteroids or NSAIDs (e.g., aspirin, ibuprofen), or other substances known to increase coagulation time (vitamins or herbal supplements, e.g., Vitamin E, garlic, gingko), from 10 days before injection to 3 days after injection.
- 9. Has a history of known liver or renal function disease/disorder or has clinically significant laboratory values at baseline.
- 10. Has a known history of allergic/anaphylactic reactions, including hypersensitivity to lidocaine or anesthetics of the amide type, or any of the device components.

- 11. Has a history of hyper- or hypo-pigmentation in the NLFs, keloid formation, or hypertrophic scarring.
- 12. Has recently lost or has the intention to lose a significant amount of weight ≥ 2 Body Mass Index (BMI) units] during the course of the study.
- 13. Has any other medical condition with the potential to interfere with the study's conduct or assessments, or increase the risk of AEs.
- 14. Has participated in a study in the last 30 days or is enrolled or plans to enroll in any other interfering investigational study during participation in the study.
- 15. Is an employee or direct relative of an employee of the investigational department in site or the sponsor.

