8.1.2.4 Indications, Contraindications and Warnings

Indications

Restylane is intended to be used for facial tissue augmentation by injections into the mid dermis to correct moderate to severe nasolabial folds.

Contraindications

- Restylane is contraindicated for patients with severe allergies manifested by a history of anaphylaxis or history or presence of multiple severe allergies.
- Restylane should not be used in the following situations:
 - Permanent implant in the same area.
 - Non-permanent implant placed in the same area during the previous 6-12 months.
 - If no information is available on the type of implant.
- Do not use in patients with bleeding disorders or patients who are taking thrombolytics or anticoagulants, or have taken inhibitors or platelet aggregation in the preceding 2 weeks.
- Restylane should not be used in or near anatomic sites where there is active skin disease, inflammation, infection or related conditions.

Warnings

- Restylane is only intended for use as an intradermal implant. Do not resterilize Restylane.
- Do not inject intravascularly. Injection into blood vessels may rarely lead to transient ischemia or even necrosis affecting the tissue supplied by the blood vessel.
- Restylane should not be mixed with other products before implantation of the device.
- The product is for single use only.
- Do not use if package is damaged.

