8.3.3 Treatment Method

Subject's NLFs will be treated with an initial injection of Radiesse on one side of the face and Restylane on the other side of the face with an optional touch-up injection at 4 weeks after initial treatment in order to achieve optimal correction. Restrictions during the study:

The following concomitant therapies will be prohibited during the study:

- No application of any new over-the-counter or prescription, oral or topical, antiwrinkle products near the NLF region during participation in this study. (Use of sunscreens and continued therapy with some cosmeceuticals, i.e., alpha hydroxyl acids, glycolic acids, retinol, or retinoic acids, is allowed if the regimen was established > 90 days prior to enrollment).
- No cosmetic facial plastic surgery or oral surgery procedures during participation in the study (i.e., orthodontia, extraction, implants).

- No dermal therapies (i.e., dermal fillers, toxin treatments, facial ablative or fractional laser, microderm abrasion, chemical peels, non-invasive skin-tightening [e.g., Ultherapy, Thermage] and surgical procedures) in the lower face and jaw line region during participation in the study.
- No systemic immunosuppressive medications or topical immunomodulatory preparations in the mid and lower face (e.g. topical steroids, calcineurin-inhibitors or imiquimod). Intranasal / inhaled steroids are allowed.
- No anti-coagulation, anti-platelet, or thrombolytic medications (i.e., warfarin), anti-inflammatory drugs (i.e., aspirin, ibuprofen), or other substances known to increase coagulation time (vitamins or herbal supplements, i.e., vitamin E, garlic, gingko) to 3 days post injection.

The following actions and treatments are prohibited as stated as long as any initial skin reddening/swelling has also subsided:

- Applying makeup and touching/pressing of the treated parts of the face up to 12 hours after treatment.
- Use of skin-irritating agents (keratolytic, antiseborrheic, anti-acne agents) on the face for at least 7 days after treatment.
- Use of pigmenting agents (self-tanning agents, depigmenting agents) on the face for at least 7 days after treatment.
- Exposure to extreme cold or heat (sauna, Turkish bath) for at least 14 days after treatment.
- Prolonged exposure to natural or artificial sources of UV radiation (e.g., sunlight or tanning booth) for at least 14 days after treatment.

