8.4 Blinding Procedures

All subjects will be treated with both Radiesse and Restylane in a split-face design. Each NLF (designated right/left) will be assigned at random via an IWRS. The treating investigator will be un-blinded to the treatment per fold. Both the subject and the blinded evaluator (must be a qualified physician) will be blinded to the randomized treatment for each NLF throughout the duration of the study.

If the subject requires a touch-up of the NLF(s) at Week 4, the same randomized product must be administered to the respective NLF(s) while maintaining the blind mentioned above.

To ensure that the blind is maintained, subjects will have their upper face masked or covered during initial and optional touch-up treatments. Subjects will be instructed not to discuss treatment and or the ratings with the blinded evaluator. Injecting investigator will not be allowed to discuss randomization assignments with the subject or the blinded evaluator(s).

It is important that the blinded evaluator(s) do not have access to any study documents that would break the blind.

Confidential and Proprietary Information. Do not disclose without authorization.

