9.2 Visit Schedule

9.2.1 Study Time Points

The planned study period is 12 Months consisting of the following visits:

- Visit 1 (Screening): Screening and Baseline Visits may be the same day (if laboratory results are available prior to treatment)
- Visit 2 (Baseline/Treatment): Day 1, Injection
- Visit 3 (Week 4 / Month 1 Post Treatment): Optional touch-up with the same randomized product
- Visit 4 (Month 3 Post Treatment)
- Visit 5 (Month 6 Post Treatment): Primary endpoint
- Visit 6 (Month 9 Post Treatment)
- Visit 7 (Month 12 Post Treatment)

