9.2.2 Data Collected

Visit 1 (Screening, Day -14 to Day 0)

The following data will be collected:

- Obtain informed consent
- Evaluate inclusion/exclusion criteria
- Subject demographics
- Vital signs: heart rate, blood pressure, and respiration rate
- Height
- Weight
- Laboratory Assessments: hematology, urine test and biochemistry
- WSRS scale assessment
- Medical history

- Concomitant Medications/Treatments
- Collect adverse events (AEs) and assess AEs

Visit 2 (Baseline/Initial Treatment, Day 1)

Screening and baseline visits may occur on the same day if laboratory test results are available prior to treatment.

The following data will be collected:

- Evaluate inclusion/exclusion criteria
- Weight
- Vital signs: heart rate, blood pressure and respiration rate
- Serum Pregnancy test for women of childbearing potential only
- Concomitant Medications/Treatments
- WSRS scale assessment
- Photograph(s) (pre-treatment)
- Randomization assignment for each NLF
- Dermal filler injections
- •
- Injection Site Reaction diary dispensed
- Collect AEs and assess AEs

Visit 3 (Week 4 / Month 1, Post Treatment; optional touchup, Day 28+ 7days)

Subjects may receive an optional touch-up injection at the 4-week post-treatment visit in order to achieve optimal correction. If touch-up is required on one or both NLFs, investigators must use the same NLF filler product as received during the initial treatment per the randomization schedule and must maintain the blind.

The following data will be collected:

- Vital signs: heart rate, blood pressure, and respiration rate

- Collect Injection Site Reaction diary and assess for AEs
- Concomitant Medications/Treatments
- If touch-up is required on one or both NLFs
 - Obtain original randomization assignment for each NLF
 - Dermal filler injections
 - -
 - Site Reaction diary dispensed
- Collect AEs and assess AEs

Visit 4 (Month 3 ± 7 days)

The following data will be collected:

- Collect Injection Site Reaction diary (if touch-up done at Visit 3) and assess for AEs
- Collect AEs and assess AEs
- Concomitant Medications/Treatments
- Photograph(s)

The following data will be collected:

- Vital signs: heart rate, blood pressure, and respiration rate
- Laboratory Assessments: hematology, urine test and biochemistry
- Weight

- WSRS scale assessment
- Photograph(s)
- Blinded evaluator GAIS

- Serum pregnancy test, for females of childbearing potential
- Collect AEs and assess AEs
- Concomitant Medications/Treatments

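### Exclusion criterion 8 looks back 10 days for anti-platelet drugs, but the protocol contraindicates Restylane, which every subject receives, for 2 weeks after them

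*Protocol*

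**What the plan says.** Criterion 8 appears in the synopsis and in section 7.3 with the same window: "from 10 days before injection to 3 days after injection". It covers anticoagulant, anti-platelet and thrombolytic drugs, anti-inflammatory drugs (aspirin is an example) and supplements that lengthen coagulation time.

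Section 8.1.2.4 lists the Restylane contraindications. Restylane is not to be used in patients currently taking thrombolytics or anticoagulants, or in those who "have taken inhibitors or platelet aggregation in the preceding 2 weeks". The only sensible reading of the last phrase is inhibitors of platelet aggregation.

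Section 8.4 makes the contraindication relevant to everyone: "All subjects will be treated with both Radiesse and Restylane in a split-face design".

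Section 8.3.3 adds a restriction on the same drug classes. It opens with "The following concomitant therapies will be prohibited during the study" and the drug item ends with "vitamin E, garlic, gingko) to 3 days post injection". It states no look-back before injection and does not say which injection it means. The schedule in section 9.2 allows an optional second injection: "Visit 3 (Week 4 / Month 1, Post Treatment; optional touchup, Day 28+ 7days".

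**The concern.** Eligibility is decided on the listed criteria. Section 7.1 requires a subject to meet every inclusion criterion and no exclusion criterion. Criterion 8 gives an explicit number of days for the drugs that section 8.1.2.4 addresses, and that number is the shorter one. A site that checks criterion 8 correctly would clear a subject to whom, under another section of the same protocol, Restylane must not be given. At stake are the safety of those subjects and the internal consistency of the protocol. The touch-up raises a smaller, related question, because section 8.3.3 leaves unclear whether its restriction applies around the second injection.

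**Working it through.** The plan gives no figure to reproduce. The check sets two time windows side by side.

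**Inputs**
- Criterion 8 look-back: 10 days (synopsis; section 7.3).
- Restylane contraindication look-back for platelet inhibitors: 2 weeks = 14 days (section 8.1.2.4).
- Injection on Day 1, in a numbering that has a Day 0; screening from Day -14 to Day 0 (section 9.2).
- Touch-up on Day 28 with up to 7 days' allowance, so Day 28 to Day 35 (section 9.2.2).

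**Gap at the initial injection**
- The contraindication covers days 1 to 14 before injection and criterion 8 covers days 1 to 10.
- Uncovered: days 11 to 14, so 14 - 10 = 4 days.
- In study days: 1 - 14 = Day -13 to 1 - 11 = Day -10.
- If a dose exactly 14 days earlier counts as outside the 2 weeks, the gap is days 11 to 13, or 3 days.

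**Which drugs are affected**

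| Agent | Section 8.1.2.4 | Criterion 8 | Result |
|---|---|---|---|
| Platelet inhibitors | preceding 14 days | 10 days | criterion shorter by 4 days |
| Anticoagulants, thrombolytics | current use | 10 days | criterion stricter |
| Corticosteroids, supplements | not mentioned | 10 days | no conflict |

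Most other Restylane contraindications are carried into section 7.3 at equal or greater strictness. For example, criterion 2 requires 12 or 18 months since a non-permanent filler, against 6 to 12 months in section 8.1.2.4. The platelet-inhibitor window is carried over in shortened form, and no reason for 10 days is given.

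**Wait if the look-back becomes 14 days**
- Last dose 14 days before the planned injection: 15 - 14 = 1 day.
- Last dose 11 days before: 15 - 11 = 4 days.
- If the dose fell after Visit 1, the wait can exceed the screening window. Example: Visit 1 on Day -14, dose on Day -10, 4-day wait. Relative to the new injection date, Visit 1 falls on Day -14 - 4 = Day -18, and rescreening is needed.

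**Touch-up**
- Look-back for a Day 28 touch-up: Day 28 - 14 = Day 14 to Day 27. For Day 35: Day 21 to Day 34.
- Latest dose compatible with a touch-up by Day 35: 35 - 15 = Day 20.
- If the section 8.3.3 restriction is tied to the initial injection only, it ends on Day 1 + 3 = Day 4, before either look-back begins.

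**The case against.** The strongest reply is that the protocol already forbids the injection. Section 8.1.2.4 is current text and binds the investigator whatever criterion 8 says. This stands. A reader might infer that the plan permits treating contraindicated subjects, and the documents do not support that. The defect is narrower: the eligibility rule does not carry a prohibition made elsewhere. The same holds for the touch-up. Section 8.1.2.4 applies to each use of Restylane, so a Restylane touch-up is not unprotected even if section 8.3.3 lapses early.

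There are further safeguards. Section 8.1.2.6 requires the doctor to discuss contraindications before treatment, the treating investigator is unblinded, section 7.1 relies on interview and judgment, and medications are recorded at Visits 1 and 2. So it would be wrong to say that only the investigator's memory protects the subject. The safeguards are still partial. Section 9.1.3.3 collects prior medication relevant to the criteria and restrictions, and a dose 12 days before injection falls outside criterion 8.

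Section 8.3.3 may also be read as barring these drugs from Visit 1 onward. That would narrow the gap without closing it. Section 9.2.1 allows "Visit 1 (Screening): Screening and Baseline Visits may be the same day (if laboratory results are available prior to treatment", and in that case all four uncovered days precede Visit 1. Beyond this the text is too ambiguous to support a count of open days.

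Harm is not demonstrated. The related risk described in section 8.1.1.4, increased bruising or bleeding, is a Radiesse precaution about patients currently using such drugs. It does not address a last dose 11 to 14 days earlier.

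Finally, a reader might conclude that every agent in criterion 8 needs a 14-day window. Section 8.1.2.4 does not support that: its 2-week period attaches to platelet inhibitors alone.

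**Conclusion.** The inconsistency is real and limited to anti-platelet drugs. Criterion 8 is about 4 days shorter than the Restylane contraindication (3 days if day 14 itself is excluded). A subject with a last dose in that interval passes eligibility and must be caught by another section.

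This rests on two assumptions: that the misprinted phrase means inhibitors of platelet aggregation, and that aspirin counts as one, although criterion 8 lists it among the anti-inflammatory drugs. The Restylane instructions for use are an appendix not available here, so the comparison uses the text of section 8.1.2.4.

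The number of subjects affected cannot be estimated. A reader might infer a bias in the Month 6 comparison, the per-protocol set or the adverse event comparison. Nothing in the documents supports that, and it is not claimed. The point is a minor safety and consistency correction that should be made.

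**What to change.** **Criterion 8, in the synopsis and section 7.3.** Set the look-back for anti-platelet drugs, naming aspirin, to at least 14 days before injection. Leave 10 days for the other listed agents.

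**Section 8.3.3.** State that the restriction runs to 3 days after each injection, and that the 14-day anti-platelet look-back also applies before a Restylane touch-up. Where possible, move the visit within Day 28 to Day 35; this works for a last dose up to Day 20. After a later dose, the Restylane touch-up is skipped. No cited text requires withholding a Radiesse touch-up in that case. The amendment should say how the Radiesse fold is handled, since touching up one fold only could leave unequal correction before Month 6.

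**Cost.** A wording amendment and an updated screening checklist. An affected subject waits up to about 4 days and occasionally needs rescreening. A few optional touch-ups may be moved or skipped. The sample size and the primary analysis method do not change.

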7.4 Removal of Subjects from Treatment or Assessment

7.4.1 Discontinuation of Subjects

A subject may discontinue from the study at any time without any penalty or loss of benefits to which the subject is otherwise entitled. Date and discontinuation circumstances will be recorded.

Subjects must be discontinued from the study by the investigator at any time for any of the following reasons:

- Withdrawal of informed consent.
- Any AE for which the subject would be unable to continue in the study.
- Any subject who becomes pregnant may complete the study and will be followed for safety assessments.

Before discontinuation, every effort should be made to ensure that the subject returns for a final study visit. In the case of loss to follow-up subjects, every effort should be made to contact any subject lost to follow-up, and all such efforts should be documented in the subject file. If appropriate, according to local regulations, Ethic Committee(s) (EC) and Competent Authorities should be informed.

7.4.2 Premature Termination or Suspension of the Study or a Study site

The study or a study site can be prematurely terminated or suspended by the sponsor. Reasons for termination of the study or a study site may include, but are not limited to, the following:

• Subject enrollment is unsatisfactory.

- The risks and benefits of continuing the study have been reassessed, and the risks outweigh any potential benefits.
- The incidence of AEs constitutes a potential health hazard to the subjects.
- New scientific data do not justify a continuation of the study.
- The investigator or study site exhibit serious and/or persistent non-adherence to the clinical study protocol and/or applicable regulatory requirements.
- The sponsor decides to terminate the study at any time for any other reason.

Furthermore, the study may be prematurely ended if the regulatory authority or the EC has decided to terminate or suspend approval for the study, the study site, or the investigator.

If the study is prematurely terminated or suspended for any reason, the investigator must inform the subjects and assure appropriate follow-up treatment. Within the timeframes noted in applicable regulations, the sponsor will promptly inform the investigators, study sites, the EC, and regulatory authorities of the termination or suspension of the study, as appropriate.

8 TREATMENTS

8.1 Investigational Product(s)

In this trial investigational products (IPs) are study product (Radiesse) and control product (Restylane).

Radiesse (1.5mL) syringe in bulk along with 27G Needle and Restylane (0.5 mL/1 mL) with a thin gauge needle (30 G x $\frac{1}{2}$ ") will be provided to the site. Radiesse will be as investigational product for this clinical use only.

8.1.1 Radiesse

See in the **Appendix 1**: Instructions for Use of Radiesse[®]

8.1.1.1 Description of Investigational Product(s)

Radiesse Injectable Implant, Merz North America, Inc.

Radiesse injectable implant is an opaque, sterile, non-pyrogenic, semi-solid, cohesive implant. The principle component is synthetic CaHA suspended in a gel carrier that consists primarily of water (sterile water for injection, United States pharmacopeia (USP)), glycerin (USP), and sodium carboxymethylcellulose (USP). Radiesse injectable implant (1.5mL syringe unit) has a CaHA particle size range of 25-45 microns and should be injected sub-dermally with a 27 gauge needle. Additional information regarding the product and administration technique will be provided in Section 8.1.1.5 of the clinical study protocol and the proposed China IFU.

8.1.1.2 *Features of the Device*

Radiesse injectable implant (dermal filler) consists of CaHA microspheres suspended in a carboxymethylcellulose gel carrier. The radiopaque CaHA microspheres are uniform in size and shape and function as a scaffold for natural collagen growth as the gel carrier is slowly replaced by the body's own connective tissue. Calcium hydroxylapatite is the primary component of bone and teeth. In particle form, it has been used for many years as inlay grafts for bone regeneration in dentistry, for the correction of oral and maxillofacial defects, as orbital implants, and coating for orthopedic prostheses¹.

8.1.1.3 Mechanism of Action

Radiesse provides immediate volumization to the injected area of the skin. Additionally, it stimulates the skin's own regeneration abilities, as new collagen is produced over the following weeks and months.

